Subjects currently enrolled onto Arms A and B will continue on Arms A and B. They will be re-consented with the revised Arm A and B consents which will reflect our updated toxicity profile. In addition, planned secondary objectives for Arms A and B (evaluation of safety and toxicity, estimation of efficacy, pharmacokinetic studies) will continue, though the analyses will only be performed based on those subjects enrolled onto Arms A and B (dose-escalation) as no subjects will be enrolled onto Arms A and B dose-expansion.

As of January 2017, this trial is being amended to revise the restaging scans and clinic visit requirements for patients who have been receiving protocol therapy for greater than 75 weeks. At the time of this amendment (Amendment 13) this study has closed to patient accrual after enrolling a total of 51 patients.

[figure not shown]

The original study schema (for Arms A and B) is shown above, and the schema for Arms C and D is shown below. Rather than proceed further with the dose-finding phase or continue to the expansion phase for Arms A and B, we will proceed directly to the dose-finding phase for Arms C and D given toxicity concerns discussed below. For Arm C and Arm D, there will be a dose-finding phase and an expansion phase. When the recommended phase II dose of intermittent BYL719 in combination with letrozole or exemestane has been determined in the dose-finding phase, an additional 10 patients will be enrolled onto Arm C and Arm D in an expansion phase of the study. The purpose of the expansion phase is to further define the safety and feasibility of BYL719 in combination with letrozole or exemestane given on two intermittent schedules, at the recommended phase II dose, and to estimate efficacy.

Dose-escalation phase

Dose-expansion phase

Patients will be eligible for either Arm C or Arm D depending on which AI they were taking before study enrollment. For both the dose-finding phase and the expansion phase, patients may have stable or progressive disease on letrozole or exemestane, and BYL719 will be added.

A treatment cycle will consist of 28 days. The regimen will consist of BYL719 in combination with letrozole or exemestane administered orally each day. Patients will be on treatment until unacceptable toxicity or progression of disease. Treatment doses and schedule are shown below:

Arm	AI dose	BYL719 schedule (dose per cohort)
A	Letrozole 2.5mg orally once daily	Days 1-28 of 28 day cycle

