6.2.1 Women age \geq 18 years

6.2.2 Willing and able to comply with scheduled visits, treatment plan and laboratory tests

6.2.3 Willing and able to consent for biopsy of locally-advanced or metastatic breast cancer prior to treatment

6.2.4 Metastatic or locally-advanced unresectable breast cancer (includes metastatic or locally-advanced unresectable breast cancer which is diagnosed while on adjuvant letrozole or exemestane)

6.2.5 Histologically documented HR+ breast cancer in either the primary or metastatic setting, as defined by ER+ or PR+; results from the local lab are acceptable. Eligibility will not be affected by HER2 status.

6.2.6 The most recent treatment prior to enrollment must be one of the following (duration of treatment \geq 2 weeks), and must have been adequately tolerated according the treating physician's judgment:

- Letrozole
- Exemestane
- Exemestane + everolimus (everolimus must be discontinued for \geq 3 weeks prior to starting study treatment)

- Letrozole or exemestane in combination with an experimental agent(s) on a clinical trial, provided that the experimental agent(s) is not a PI3K inhibitor or AKT inhibitor (see Section 6.2.3) (experimental agent(s) must be discontinued for ≥ 3 weeks prior to starting study treatment)

6.2.7 Any number of prior endocrine therapies (including tamoxifen, fulvestrant and/or aromatase inhibitors in either the adjuvant or metastatic setting) and any number of prior chemotherapy regimens. Anti-cancer systemic therapy, such as chemotherapy or biologics or endocrine therapy, other than the AI, must be discontinued for ≥ 3 weeks prior to starting study treatment.

6.2.8 For the dose-finding phase, patients may have stable disease OR progression of disease on the most recent treatment. For the expansion phase, patients must also have stable disease OR progression of disease on the most recent treatment. Progression of disease is defined as new or worsening disease on objective imaging. Progression of disease includes recurrence diagnosed while on adjuvant letrozole or exemestane.

6.2.9 Postmenopausal women, as defined by one of the following (estradiol assay cutoff takes into account that the patient is on aromatase inhibitor therapy):

- Age ≥ 55 years and one year or more of amenorrhea
- Age < 55 years and one year or more of amenorrhea, with an estradiol assay within the post-menopausal range

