Based on our ongoing experience with our tumor biopsy study to evaluate molecular mechanisms of resistance in patients with HER2+ disease (MSKCC IRB # 06-163, [name] - PI), we anticipate that it will be feasible to obtain a pre-treatment biopsy in at least 80% of patients (~30 patients assuming total accrual of 38 patients). Due to logistical issues, such as lack of sufficient viable cells in the biopsy sample, it is possible that a viable pre-treatment biopsy sample may not be obtained in several patients.

In order to determine if pharmacodynamic markers of PI3K pathway hyperactivation and inhibition predict for PFS, proteomic analysis of pre-treatment and Day 15 on-treatment biopsies will be performed. The Spearman's rank correlation of inpatient percent change in PI3K pathway activation signature (measured as a continuous variable) with percent tumor volume change at 8 week CT scan (measured as a continuous variable) will be calculated to evaluate whether pharmacodynamic markers of PI3K pathway inhibition are predictive of response to therapy.

We anticipate that it will be feasible to obtain a Day 15 on-treatment biopsy in at least 50% of patients (~19 patients assuming total accrual of 38 patients).

To evaluate mechanisms of AI resistance, the analysis will include pre-treatment tumor biopsies obtained in patients who had POD on an AI at the time of study consent, on-treatment biopsies, as well as optional post-progression biopsies. We estimate that this will include about half of patients in the dose-finding phase (because those with stable disease will be excluded), and all patients in the expansion phase who have a viable pre-treatment biopsy sample.

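### Does the forecast that every expansion patient with a viable biopsy joins the AI-resistance set conflict with expansion eligibility in a way that needs a change?

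*Combined protocol and SAP*

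**What the plan says.** Section 14.5 of the combined protocol and SAP defines the material for the AI-resistance analysis. For samples taken before treatment, the set consists of "pre-treatment tumor biopsies obtained in patients who had POD on an AI at the time of study consent". On-treatment and optional post-progression biopsies are listed as well, with no visible condition on progression.

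The next sentence forecasts the size of the set. For the first phase it reads: "We estimate that this will include about half of patients in the dose-finding phase (because those with stable disease will be excluded". For the second phase it counts "all patients in the expansion phase who have a viable pre-treatment biopsy sample". Earlier in the same section the plan expects that "it will be feasible to obtain a pre-treatment biopsy in at least 80% of patients".

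Eligibility is in Section 6.2.8. For dose-finding: "For the dose-finding phase, patients may have stable disease OR progression of disease on the most recent treatment". For expansion: "For the expansion phase, patients must also have stable disease OR progression of disease on the most recent treatment". Section 1.0 agrees: "For both the dose-finding phase and the expansion phase, patients may have stable or progressive disease on letrozole or exemestane". Section 4.0 says the same for Arms C and D. No section limits expansion to patients with progressive disease.

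**The concern.** Section 14.5 lowers the dose-finding count because stable patients drop out, but makes no reduction for expansion. The two phases can differ in this way only if expansion takes no stable patients, and Section 6.2.8 sets the same condition for both. A reader of 14.5 could therefore expect more pre-treatment samples from AI-resistant tumours than the rule can supply.

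The more serious possibility is that someone treats the forecast as the inclusion rule. Tumours that had not progressed on the AI would then enter a set meant to show mechanisms of resistance, and any contrast in the sequencing results would be diluted.

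**Working it through.** **Inputs**
- Planned total for Arms C and D: about 38 (Sections 14.1 and 14.5).
- Planned expansion size, E: 10 per arm, so 20 (Section 14.3). Section 4.0 reports the Arm C expansion on hold, so E = 10 is the second case.
- Yield of viable pre-treatment samples, v: taken as 0.80. This is an assumption. Section 14.5 gives 80% as a floor for obtaining a biopsy, and adds that some samples may not be viable.
- Share of expansion patients who are stable at entry, s: not given. The range used is 0 to 0.75. The only anchor is the estimate in 14.5 that about half of dose-finding patients qualify under the same entry condition, which points to s = 0.50.

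**The plan's own figures**
- Pre-treatment biopsies: 0.80 × 38 = 30.4; the plan states about 30.
- Day 15 biopsies: 0.50 × 38 = 19.0; the plan states about 19.

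Both reproduce. The plan gives no headcount for the AI-resistance set, only the shares.

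**Excess in the forecast**

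The forecast counts E × v expansion samples. The progression rule admits E × v × (1 − s). The excess is the difference, E × v × s.

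| s | E = 20 (16 forecast) | E = 10 (8 forecast) |
|---|---|---|
| 0 | 0 | 0 |
| 0.25 | 20 × 0.80 × 0.25 = 4 | 2 |
| 0.50 | 8 | 4 |
| 0.75 | 12 | 6 |

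The excess does not depend on the number of dose-finding patients, and it scales in proportion to v.

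**Could the forecast be exactly right?** It is right only if every expansion patient with a viable sample had progressed. If 16 patients were each stable independently with probability s, the chance of that is (1 − s)^16: 0.185 at s = 0.10, 0.010 at s = 0.25, and about 0.00002 at s = 0.50. So the forecast is probably too high if expansion resembled dose-finding. It is correct if expansion in practice drew only patients with progression, which Section 6.2.8 allows but does not require.

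**What uses the number?** The dose-finding rules (Section 9.5 as headed, and 14.2), the expansion safety rules (14.3) and the efficacy estimates (14.4) make no reference to it. Section 14.5 attaches no power or precision statement to it and describes the correlative work as mainly descriptive.

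**The case for a change.** The strongest argument for a change is that 14.5, read quickly, offers two analysis sets for expansion: patients with progression only, or everyone with a viable sample. One or two sentences would remove the doubt. The reason given for excluding stable patients is also attached to dose-finding alone, so a reader might think the authors meant expansion to be handled differently.

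Some of this stands. The estimate does not follow from the eligibility criteria, and nothing in the documents rescues it. But the condition on progression at consent comes before the forecast and is not tied to a phase, whereas the other sentence is presented as an estimate. A rule governs over an estimate of what the rule will yield. The same rule has to be applied patient by patient in dose-finding, so progression status at entry must be established anyway, and Section 6.2.8 defines progression by objective imaging. Nothing in the documents suggests that the forecast was meant for selecting samples.

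Correcting the forecast would also gain little now. Section 1.0 records that "this study has closed to patient accrual after enrolling a total of 51 patients", so the number of qualifying samples can be counted instead of predicted.

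The mixed entry status might also prompt a request to split the expansion efficacy results into stable and progressive patients. That would be an addition and not a correction: the per-arm estimates in 14.4 already match the objective in Section 2.2. At 50% stable, each arm would have about 10 × 0.5 = 5 patients with progression, and an exact 95% interval for 2 of 5 runs from 5% to 85%.

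**Conclusion.** The inconsistency is genuine but editorial. Section 14.5's estimate for expansion is unsupported by Section 6.2.8, and it is too high if any stable expansion patient had a viable sample. The size cannot be fixed from the documents. It is 0 if no such patient was stable, and 8 of 16 samples (or 4 of 8 with a single expansion arm) if half were, assuming an 80% viable yield and a stable share borrowed from dose-finding.

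The inclusion rule for pre-treatment samples is stated and workable, and following it keeps stable tumours out of the pre-treatment set in both phases. The count feeds no decision, and the true number is obtainable because accrual is closed. Analysts should apply the rule and report how many samples met it. The plan need not be amended for this.

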15.1 RESEARCH PARTICIPANT REGISTRATION AND RANDOMIZATION PROCEDURES

15.2 Research Participant Registration

Confirm eligibility as defined in the section entitled Criteria for Patient/Subject Eligibility.

Obtain informed consent, by following procedures defined in section entitled Informed Consent Procedures.

During the registration process registering individuals will be required to complete a protocol specific Eligibility Checklist.

All participants must be registered through the Protocol Participant Registration (PPR) Office at Memorial Sloan-Kettering Cancer Center. PPR is available Monday through Friday from 8:30am – 5:30pm at [contact]. Registrations must be submitted via the PPR Electronic Registration System (<http://ppr/>). The completed signature page of the written consent/RA or verbal script/RA, a completed Eligibility Checklist and other relevant documents must be uploaded via the PPR Electronic Registration System.

15.3 Randomization

Randomization will not be necessary for this study. Patients will be eligible for only one of the two arms depending on which AI (letrozole or exemestane) they were taking before study enrollment. Patients will not be randomized to one of the two arms.

16.1 DATA MANAGEMENT ISSUES

A Research Study Assistant (RSA) will be assigned to the study. The responsibilities of the RSA include project compliance, data collection, abstraction and entry, data reporting, regulatory monitoring, problem resolution and prioritization, and coordination of the activities of the study team.

The Clinical Research Database (CRDB) will be used for data collection. The data will be reported to the institution (IRB) and the drug manufacturer (Novartis) as appropriate.

Tumor slides will be stored in the breast surgery laboratory. Results from laboratory studies will include photomicrographs of IHC studies, computer files of sequencing data, and computer files from microarray analyses. These files will be stored on the Department of Medicine server. Documentation linking patient identifiers and patient samples and results will be securely maintained in the CRDB with access limited to study investigators.

It is estimated that 2 patients will be accrued per month and it will take up to two years to accrue.

16.2 Quality Assurance

Routine registration reports will be generated to monitor patient accruals and completeness of registration data. Routine data quality reports will be generated to assess missing data and inconsistencies. Accrual rates and extent and accuracy of evaluations and follow-up will be monitored periodically throughout the study period and potential problems will be brought to the attention of the study team for discussion and action.

Random-sample data quality and protocol compliance audits will be conducted by the study team, at a minimum of two times per year, more frequently if indicated.

16.3 Data and Safety Monitoring

The Data and Safety Monitoring (DSM) Plans at Memorial Sloan-Kettering Cancer Center were approved by the National Cancer Institute in September 2001. The plans address the new policies set forth by the NCI in the document entitled "Policy of the National Cancer Institute for Data and Safety Monitoring of Clinical Trials" which can be found at:

<http://www.cancer.gov/clinicaltrials/learningabout/patientsafety/dsm-guidelines/page1>. The

DSM Plans at MSKCC were established and are monitored by the Office of Clinical Research. The MSKCC Data and Safety Monitoring Plans can be found on the MSKCC Intranet at:

[http://smskpsps9/dept/ocr/OCR%20Website%20Documents/Clinical%20Research%20Quality%20Assurance%20\(CRQA\)/MSKCC%20Data%20and%20Safety%20Monitoring%20Plan.pdf](http://smskpsps9/dept/ocr/OCR%20Website%20Documents/Clinical%20Research%20Quality%20Assurance%20(CRQA)/MSKCC%20Data%20and%20Safety%20Monitoring%20Plan.pdf).

There are several different mechanisms by which clinical trials are monitored for data, safety and quality. There are institutional processes in place for quality assurance (e.g., protocol monitoring, compliance and data verification audits, therapeutic response, and staff education on clinical research QA) and departmental procedures for quality control, plus there are two institutional committees that are responsible for monitoring the activities of our clinical trials programs. The committees: *Data and Safety Monitoring Committee (DSMC)* for Phase I and II clinical trials, and *the Data and Safety Monitoring Board (DSMB)* for Phase III clinical trials, report to the Center's Research Council and Institutional Review Board.

17.1 PROTECTION OF HUMAN SUBJECTS

Prior to the enrollment of each patient, the risks, benefits and objectives of the study will be reviewed with the participant, including a discussion of the possible toxicities and side effects. Alternative treatment options, including non-protocol treatment options, will be discussed with the patient. It will be reviewed that participation in this clinical trial is voluntary and that the patient may withdraw consent at any time. The study is designed with careful safety monitoring for toxicity including physician visits approximately every 4 weeks and approximately every 8 weeks at minimum for patients on study under Amendment 13 of the protocol. Every effort will be made to keep study records private. Neither the patient's name nor anything else that could identify the patient will be used in any reports or publications that result from this study. Trained staff at Memorial Sloan-Kettering Cancer Center, the Food and Drug Administration, or the drug manufacturer, Novartis, will be able to review the medical records if necessary. The financial costs of the study will be discussed with the patient; BYL719 will be provided free of charge. The cost of the pharmacokinetic studies and correlative research on tumor biopsies will be covered by RNB.

17.2 Privacy

Medical information is confidential. The participant's personal identity will not be used in reports that are written about the research. The MSKCC IRB/PB will review all requests for research performed involving biospecimens ascertained through this protocol. Blood and tissue samples will be stored with a code linked to the patient's medical record. With the permission of the IRB/PB, research studies on cellular, genetic, immunologic, or other features of tumor or normal samples may be performed with no names attached to the samples but linked by codes to personal identifiers. The results of any research using blood or tissues will not be placed in the medical record.

MSKCC's Privacy Office may allow the use and disclosure of protected health information pursuant to a completed and signed Research Authorization form. The use and disclosure of protected health information will be limited to the individuals described in the Research Authorization form. A Research Authorization form must be completed by the Principal Investigator and approved by the IRB and Privacy Board (IRB/PB).

The consent also indicates that samples and genetic information collected may be shared with other qualified researchers. Such information will not include identifying information such as name. It is also stated in the consent and Research Authorization that research data (e.g. genomic sequence) may be placed into databases monitored by the National Institutes of Health, and may be made accessible to investigators approved by the U.S. government.

The requirements for submission of genotype/phenotype data into the NIH GWAS Repository (or any other public database) will be outlined in the biospecimen analysis application, i.e. IRB Biospecimen Correlative Protocol.

17.3 Serious Adverse Event (SAE) Reporting

An adverse event is any undesirable sign, symptom or medical condition occurring after starting study drug (BYL719), even if the event is not considered to be related to study drug. Information about all adverse events, whether volunteered by the subject, discovered by investigator questioning, or detected through physical examination, laboratory test or other means, will be collected, recorded and followed as appropriate. Medical conditions/diseases present before starting study treatment are only considered adverse events if they worsen after starting study treatment (any procedures specified in the protocol). Adverse events occurring before starting study treatment but after signing the informed consent form are recorded. Abnormal laboratory values or test results constitute adverse events only if they induce clinical signs or symptoms or require therapy, and are recorded.

A serious adverse event (SAE) is an undesirable sign, symptom or medical condition which:

1. is fatal or life-threatening,
2. required or prolonged hospitalization,
3. results in persistent or significant disability/incapacity,
4. constitutes a congenital anomaly or a birth defect, or
5. is medically significant, may jeopardize the subject and may require medical or surgical intervention to prevent one of the outcomes listed above.

Events not considered to be serious adverse events are hospitalizations for:

- routine treatment or monitoring of the studied indication, not associated with any deterioration in condition,
- treatment, which was elective or pre-planned, for a pre-existing condition that did not worsen,
- treatment on an emergency, outpatient basis for an event not fulfilling any of the definitions of serious given above and not resulting in hospital admission.

Any serious adverse event occurring after the patient has provided informed consent, has started taking the study medication, and until 30 days after the patient has stopped study participation must be reported. This includes the period in which the study protocol interferes with the standard medical treatment given to a patient (e.g. treatment withdrawal during washout period, change in treatment to a fixed dose of concomitant medication). The period after discontinuing study drug may be extended if there is a strong suspicion that the drug has not yet been eliminated.

Hyperglycemia is an adverse event of interest. Grade 3 or 4 hyperglycemia must be reported to the IRB and Novartis.

Any SAE must be reported to the IRB/PB as soon as possible but no later than 5 calendar days.

The IRB/PB requires a Clinical Research Database (CRDB) SAE report be submitted electronically to the SAE Office at [contact]. The report should contain the following information:

Fields populated from CRDB:

- Subject's name (generate the report with only initials if it will be sent outside of MSKCC)
- Medical record number
- Disease/histology (if applicable)
- Protocol number and title

Data needing to be entered:

- The date the adverse event occurred
- The adverse event
- Relationship of the adverse event to the treatment (drug, device, or intervention)
- If the AE was expected
- The severity of the AE
- The intervention
- Detailed text that includes the following
 - A explanation of how the AE was handled
 - A description of the subject's condition
 - Indication if the subject remains on the study
 - If an amendment will need to be made to the protocol and/or consent form.

The PI's signature and the date it was signed are required on the completed report.

For IND/IDE protocols:

The CRDB AE report should be completed as above and the FDA assigned IND/IDE number written at the top of the report. If appropriate, the report will be forwarded to the FDA by the SAE staff through the IND Office.

17.2.1

The principal investigator has the obligation to report all serious adverse events to the IRB, FDA (all correspondence with the FDA must go through the MSKCC IND Office), and Novartis Pharmaceuticals Drug Safety and Epidemiology Department (DS&E).

SAEs will be reported to Novartis concurrent to MSKCC CRDB SAE Report Form using the MSKCC CRDB SAE Report Form.

The investigator must complete the SAE Report Form and Novartis SAE fax coversheet in English, assess the relationship to study treatment and send the initial completed SAE Report Form and Novartis SAE coversheet by [contact] within 24 hours of learning of its occurrence (excluding weekends and holidays) to the local Novartis DS&E Department. The investigator must then ensure that the form and coversheet are accurately and fully completed with follow-up information and fax those to Novartis DS&E Department within 2 to 3 calendar days for deaths or life-threatening events and 5 calendar days for other serious

adverse events. The original and the duplicate copies of the SAE Report Form, Novartis SAE coversheet, and the fax confirmation sheet must be kept at the study site.

Follow-up information should describe whether the event has resolved or continues, if and how it was treated, and whether the patient continued or discontinued study participation. The SAE Report Form, Novartis SAE coversheet, and fax confirmation sheet must be retained.

